3.2.2 Exclusion Criteria

A subject will **not** be eligible for inclusion in this study if any of the following criteria apply:

Current or Past Medical History

- 1. Functional Class IV as defined by ACR classification of functional status in RA.
- 2. History of significant systemic involvement secondary to RA (e.g., vasculitis, pulmonary fibrosis, or Felty's syndrome).
- 3. History of malignancy or carcinoma in situ within the 5 years before Screening or a history of melanoma. Patients with history of excised or adequately treated non-melanoma skin cancer are eligible.
- 4. Evidence of clinically significant uncontrolled concurrent diseases such as cardiovascular, endocrine, hematologic, hepatic, immunologic, metabolic, urologic, pulmonary, neurologic, dermatologic, psychiatric, renal, and/or other major diseases.
- 5. History of recurrent clinically significant infections.
- 6. Current active infection or serious local infection (e.g., cellulitis, abscess) or systemic infection (e.g., pneumonia, septicemia) within 3 months before randomization.
- 7. Fever (body temperature > 38°C) or symptomatic viral or bacterial infection within 14 days before randomization.
- 8. History of drug or alcohol abuse (as defined by the Investigator) within the 1 year before Screening.
- 9. History of severe allergic or anaphylactic reactions to other biologic agents.
- 10. History of allergies to murine protein.
- 11. Surgery within 3 months before randomization (other than minor cosmetic surgery or minor dental procedures) or plans for a surgical procedure during the Treatment Period or Follow-up Period.

Salix Pharmaceuticals, Inc. Protocol: C2013-0302

- 12. History of malaria; patients with a history of travel to a malaria-endemic region within 4 months before randomization may be considered for enrollment upon consultation with the Sponsor regarding confirmation of no active disease via a polymerase chain reaction (PCR). Patients should not plan to travel to a malaria-endemic region throughout the duration of the study, including Screening and the 4-week Follow-up Period.
- 13. History of tuberculosis or latent infection currently undergoing treatment.

Treatment History

- 14. This criterion was removed in Protocol Amendment #3.
- 15. Treatment with another investigational agent, investigational device, or approved therapy for investigational use within the 4 weeks before randomization or within 5 half-lives of the investigational agent (longer of the two).
- 16. Treatment regimen with prednisone that is either over 10 mg/day (or equivalent dose of another corticosteroid) or is not taken at a stable dose of \leq 10 mg/day for at least 4 weeks before randomization.
- 17. Intra-articular corticosteroid injection(s) within 4 weeks before randomization.
- 18. Current use of opioids or other narcotics. Note: Patients receiving nonsteroidal anti-inflammatory drugs (NSAIDS) or the following opioids (tramadol, codeine and oral acetaminophen/codeine combination) at stable doses for at least 2 weeks prior to randomization will be eligible for inclusion.
- 19. Any live immunization/vaccination, including against Herpes zoster, within 4 weeks before randomization. Live vaccinations must also be avoided throughout the study.

Laboratory Values

- 20. Abnormal laboratory value at Screening or Day -1 considered clinically significant (as determined by the Investigator), or:
 - Serum creatinine > 1.6 mg/dL

- Aspartate aminotransferase (AST) or alanine aminotransferase (ALT) $> 1.5 \times ULN$
- Platelet count $< 100,000/\mu L$
- Hemoglobin < 8.5 g/dL
- Absolute neutrophil count (ANC) $< 2.0 \times 10^3 / \mu L$
- 21. Women of childbearing potential who test positive for a serum pregnancy test at Screening or a urine pregnancy test within 12 hours before randomization.

General/Compliance

- 22. Positive for hepatitis C virus (HCV) antibody or hepatitis B surface antigen (HBsAg) (Note: patients with positive HCV antibody may be considered for enrollment upon consultation with the Sponsor regarding confirmation of no active disease via a PCR test).
- 23. Positive for human immunodeficiency virus (HIV) antibody.
- 24. Positive QuantiFERON®-TB Gold test (QFT) (Note: If the QFT result is indeterminate and the chest X-ray is without clinically significant findings, a second QFT may be performed. If the second QFT result is negative, the patient may be considered for enrollment. If the second QFT is positive or indeterminate, the patient is ineligible.)
- 25. Current enrollment in any other study with an investigational agent, investigational device, or approved therapy for investigational use).
- 26. Previous exposure to SAN-300
- 27. Unwillingness or inability to comply with the requirements of this Protocol, including the presence of any condition (physical, mental, or social) that is likely to affect the patient's returning for follow-up visits on schedule
 - NOTE: Patients who cannot tolerate the magnetic resonance imaging (MRI) procedures due to physical or other limitations may be enrolled in the study

- 28. Other unspecified reasons that, in the opinion of the Investigator or the Sponsor, make the patient unsuitable for enrollment
- 29. Blood donation (450 mL or more) within 1 month before Screening
- 30. Nursing mothers or women who are planning to become pregnant during the study

3.3 Treatments

SAN-300 for Subcutaneous Injection

The Investigational Product for SC injection (SAN-300-F02) is manufactured by IntegrityBio, Inc. of Camarillo, CA, USA under Good Manufacturing Practice (GMP). The SAN-300-F02 drug product is formulated with 180 mg/mL anti-VLA-1 mAb, 30 mM histidine, 250 mM sorbitol, and 0.01% polysorbate 20 at pH 6. The drug product is filled to a total volume of 1 mL in a 2-mL USP type I glass vial with a 13-mm chlorobutyl stopper and a 13-mm aluminum seal. The storage temperature for the drug product is 2 °C to 8 °C, protected from light. For SC administration, the appropriate volumetric dose of SAN-300 will be injected with a 27-gauge, ½ inch syringe needle on a weight-based calculation. More than one SC injection may be required (maximum volume of 1.2 mL per injection) depending on the total dose administered and the weight of the individual patient.

Placebo for Subcutaneous Injection

For SC administration, placebo is 30 mM histidine, 250 mM sorbitol, 0.01% polysorbate 20, and 3 μg/mL riboflavin at pH 6, with a 1-mL fill in the same container closure system as the drug product. This was also manufactured by IntegrityBio, Inc. of Camarillo, CA, USA under GMP. The appropriate volumetric dose of placebo will be injected with a 27-gauge, ½ inch syringe needle via SC injection. The volume of placebo administered SC will match the volume according to the weight-based calculations as if SAN-300 were to be administered. More than one SC injection may be required (maximum volume of 1.2 mL per injection) depending on the total dose administered and the weight of the individual patient. The intended storage temperature for the placebo product is 2 °C to 8 °C, protected from light.

3.4 Randomization and Unblinding

Fixed allocation will be used to randomize subjects in a ratio of three on SAN-300 to one on placebo 3:1 within each cohort of approximately 8 total subjects using a randomization code generated by an Interactive Web Response System (IWRS). Central randomization will be utilized for this study.

Only in the case of an emergency, when knowledge of the study drug is essential for the clinical management or welfare of the subject, will the investigator be allowed to unblind a subject's treatment assignment. If the investigator breaks the blind for an individual subject, the reason must be in the subject's source documents and the subject will be removed from the study.

3.5 Sample Size

There is no sample size calculation, as this study is not intended to be powered to demonstrate efficacy. Results from this study will be used to design future efficacy studies.

After safety review it was decided that no dose adjustment is needed for optional cohort F, and as a result 41 subjects were randomized into study.

4 GENERAL CONSIDERATIONS FOR DATA ANALYSIS

All statistical testing will be two-sided with an alpha level of 0.05. Any p-values displayed will be rounded to four decimal places, with p-values below 0.0001 displayed as '<.0001', and p-values above 0.9999 displayed as '>.9999'.

Categorical variables will be summarized by frequency counts and percentages for subjects in each category. Percentages will contain one decimal place. In cases of zero frequency counts, the percentage will not be reported.

Continuous variables will be summarized with the number of observations (n), mean, standard deviation (SD), median, minimum, and maximum. The mean and median will be presented to one decimal place more than the captured data. The SD will be presented to two decimal places

more than the captured data. The minimum and maximum will be presented to the same precision as the captured data.

Study day will be calculated as follows:

- Assessments/events prior to the first dose date, study day will be the assessment date minus the first dose date.
- Assessments/events on or after the first dose date, study day will be the assessment date minus the first dose date plus one.

Baseline is defined to be the last non-missing assessment (including assessments measured at unscheduled visits) before receiving the first dose of the study medication.

End of treatment (EOT) value is defined as last available post-baseline value during the treatment period.

Subjects will be identified in listings by center number and subject number. Unless otherwise specified, all listings will be sorted by randomized treatment, subject identification number and visit (if applicable).

Efficacy analysis will be performed on the Intent-to-Treat (ITT) population by treatment group to which subjects were randomized. Safety analysis will be performed on the Safety population by treatment received.

Parameters presented by "treatment group" will display the patients on SAN-300 from each cohort and the pooled patients on placebo, unless otherwise indicated.

4.1 Analysis Populations

The ITT population is defined as all randomized patients who received at least one dose of a study drug. Patients in the ITT Population will be analyzed according to the treatment to which they were randomized.

The Per Protocol (PP) Population is defined as all patients in the ITT Population except for those who failed to meet Inclusion Criterion 4; or met Exclusion Criteria 1 and 2.

The Safety Population is defined as all patients who received at least one dose of a study drug; this population will be used for the safety analysis. Patients in the Safety Population will be analyzed according to the treatment they received.

The summaries and analyses of baseline characteristics and efficacy will be performed for the ITT Population. All efficacy analyses will also be performed on the PP Population as a sensitivity analysis. All safety analyses will be performed on the Safety Population.

4.2 Protocol Deviation

All protocol deviations will be listed.

5 SUBJECT DISPOSITION

Subject disposition will be summarized for all randomized subjects and will include the number of subjects randomized; number and percentage of subjects who completed or prematurely discontinued the study, classified by reasons for premature discontinuation; the number of subjects randomized at each study site; and the number and percentage of subjects who completed or discontinued the study at each study site.

The number and percentages of subjects in each population and reason for exclusion from population will be summarized for all randomized subjects.

6 DEMOGRAPHICS AND BASELINE DISEASE CHARACTERISTICS

6.1 Demographics

Demographics listed below will be summarized descriptively by treatment group and overall using the ITT population.

• Age (years);

21

- Sex (male/female);
- Ethnicity (Hispanic or Latino/not Hispanic or Latino);
- Race (American Indian or Alaskan Native, Asian, Black or African-American, Native Hawaiian or Pacific Islander, and White); where subjects who identified more than one race will be categorized as "Multiple";
- Height (cm);
- Weight (kg); and
- Body mass index $(kg/m^2) = (Weight in kg)/(Height in m)^2$.

6.2 Baseline Characteristics

Baseline characteristics listed below will be summarized descriptively by treatment group and overall using the ITT population.

- Disease Activity Score with 28-joint count using C-reactive protein (DAS28-CRP), ACR
 Core Set Measurements, the Health Assessment Questionnaire Disability Index (HAQ-DI)
- MRI score using the Outcome Measures in Rheumatology Clinical Trials (OMERACT)
 RA MRI scoring (RAMRIS) system
- Visual Analog Scale (VAS) score
- Duration of RA disease from initial diagnosis
- Use of Methotrexate, Chloroquine, NSAIDS, Corticosteroid

6.3 Medical History

Medical history data will be coded using the Medical Dictionary for Regulatory Activities (MedDRA) version 19.0 or later and will be listed. In addition, Medical history data will be summarized by system organ class and preferred term. A separate detailed RA history also be summarized descriptively by treatment group.

7 EFFICACY ANALYSIS

Efficacy evaluations will consist of changes from baseline in the Disease Activity Score with 28-joint count using C-reactive protein (DAS28-CRP), ACR Core Set Measurements, the Health Assessment Questionnaire – Disability Index (HAQ-DI), and magnetic resonance imaging (MRI) of the hand and wrist most clinically affected by RA. Each MRI will be scored using the OMERACT RAMRIS system.

7.2 Secondary Efficacy Analysis

The percentages of patients achieving a DAS28-CRP \leq 3.2 and \leq 2.6 will be compared across treatment groups using the chi-square test.

The ACR Core Data Set is a standardized measure of arthritis activity consisting of seven measures, three made by an assessor, three made by the patient, and one laboratory value (CRP or erythrocyte sedimentation rate [ESR]), as shown below:

- Swollen and tender joint assessment (assessor refer to Appendix 6 of Protocol (Amendment 5))
- Physician's global assessment of disease activity (assessor)
- Patient assessment of pain (patient)
- Patient's global assessment of disease activity (patient)
- Patient's assessment of physical function as measured by Health Assessment
 Questionnaire (HAQ) (patient refer to Appendix 7 of Protocol (Amendment 5))
- CRP or ESR (laboratory test)

The assessor will be an experienced rheumatology clinical assessor.

All components of the ACR Core Set will be summarized using descriptive statistics and presented by time point and treatment group. The percentages of subjects achieving ACR20, ACR50, or ACR70 responses will be compared across treatment groups using the chi-square test. MRI data will be summarized across the treatment groups for each time point. All MRI data will be presented for individual patients in data listings.

All efficacy assessments will be presented for individual patients in data listings.

Additional analyses may be performed, as needed, to fully evaluate potential efficacy signals and evidence of clinical benefit.

7.2.1 Pharmacokinetics of SAN-300

Statistical analysis (including exploratory data analysis and population modeling) for pharmacokinetics of SAN-300 will be described in detail in the PSAP document. The PSAP will be finalized prior to database lock.

7.3 Exploratory Efficacy Analysis

An exploratory analysis of the primary endpoint will be performed using analysis of covariance (ANCOVA) model with treatment as factor and baseline DAS28-CRP and HAQ-DI scores as covariates. Normality of the mean change from baseline of DAS28-CRP data will be tested and if necessary transformation such as but not limited to logarithmic transformation could be applied.

The ratios of the least squares (LS) geometric means and 95% confidence intervals (CI) for mean change from baseline of to the EOT Visit for DAS28-CRP from the administration of SAN-300 ("test") relative to the administration of Placebo ("reference"), test/reference, will be calculated.

Comparison analysis for ACR20, ACR50, or ACR70 responses for pooled treatment group against placebo will be conducted using Fisher exact test. Bar chart will be plotted by SAN-300 treatment regimen to show if there is linear relationship between ACR20, ACR50, and ACR70 and SAN-300 dose level and frequency.

In addition, logistic regression model with treatment regimen as ordinal variable will be performed on to compare percentage of subjects achieved ACR20, ACR50, and ACR70 responses at the EOT Visit. Predictor variables may include swollen joint count at screening, tender joint count at screening, and methotrexate use (yes/no).

Statistical analyses will be performed and statistical tables will be generated using Statistical Analysis Software (SAS) version 9.3 or higher. Statistical significance will be assessed at the two-sided 5% level.

8 SAFETY PRESENTATION

8.1 Extent of Exposure

The number of subjects administered study drug and the extent (duration) of exposure to study drug will be summarized descriptively by treatment group (n, mean, median, SD, minimum, and maximum values). Extent of exposure is defined as last dose of study drug – first dose of study drug +1. Additionally, number and percent by duration category by week for the first 4 weeks and then by 2-week intervals thereafter will also be summarized by treatment group.

8.2 Adverse Events

Adverse events will be coded using the MedDRA version 19.0 or later coding dictionary. If an adverse event is not coded then the verbatim investigator text will be listed at the end of each applicable summary table.

8.2.1 Treatment-Emergent Adverse Events

A treatment-emergent adverse event (TEAE) is defined as any AE started post-treatment. Summary tables will include number of subjects with treatment-emergent AEs and as percentage of number of subjects in the treatment group. The number of serious TEAEs will be summarized in the appropriate summary table. Summary tables will also be presented for the frequency of AEs by MedDRA-preferred term and severity of AE. Severity of AEs will be based on the scale as indicated in Section 8.2.2.

The subset of AEs that are considered by the Investigator to have a possible or definite relationship to study medication will be considered as treatment-related AEs. If the Investigator does not specify the relationship of the AE to study medication, the AE will be considered as treatment-related. The incidence of AEs and TEAEs will be tabulated per treatment. AEs will also be summarized by severity, using the categories described in Section 8.2.2.

26

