9.1 Operating Definitions for Assessing Safety

9.1.1 Adverse Event

An AE is any untoward medical occurrence in a patient or clinical investigation patient administered a study product and which does not necessarily have a causal relationship with the treatment.

An AE can therefore be any unfavorable and unintended sign (that could include a clinically significant abnormal laboratory finding), symptom, or disease temporally associated with the use of a study product, without any judgment about causality (i.e., whether or not considered related to the study product).

Additionally, an event that is associated with study participation (regardless of administration of or relationship to study drug) should be treated as a reportable adverse event for this protocol (e.g., complications resulting from the taking of a blood sample or performance of a protocol required procedure).

Amendment 5: 28 Mar 2016

An AE does include the following:

- Exacerbation or worsening of a pre-existing illness.
 - NOTE: if the pre-existing illness is the disease under study, then "exacerbation" refers to an unexpected worsening from the condition at baseline.
- Increase in frequency or intensity of a pre-existing episodic event or condition.
- Condition detected or diagnosed after study product administration even though it may have been present prior to the start of the study.
- Symptom associated with disease not previously reported by the patient

An AE does not include the following:

- Medical or surgical procedures (e.g., surgery, endoscopy, tooth extraction, transfusion) as event terms; the condition that led to the procedure is the AE if it meets the definition of an AE.
- Situations where an untoward medical occurrence has not occurred (e.g., hospitalization for cosmetic elective surgery; and social and/or convenience admissions).
- Overdose of either study product or concurrent medication without any signs or symptoms.
- Symptoms associated with disease, which are consistent with the patient's usual clinical course; unless the subject experiences worsening of their symptom(s) or the symptom(s) meet the criteria for an SAE. Any medical condition present at the time of screening but does not worsen during the course of the study should be recorded as medical history.

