9.3.1 Time Period for Detecting and Reporting of AEs and SAEs

From the time of informed consent through study completion/withdrawal, including the follow-up period.

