2.2.2 Safety Endpoints

The safety and tolerability will be assessed by the following endpoints:

- Incidence of treatment-emergent adverse events (TEAEs).
- Changes from baseline in clinical laboratory parameters.

- Changes from baseline in vital sign measurements.
- Changes from baseline in electrocardiogram measurements.
- Symptom driven physical examinations

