8.2.4 Treatment-Emergent Serious Adverse Events

Any AE reported as serious in the Case Report Form (CRF) will be reported as a serious adverse event (SAE). The clinical database will be reconciled with the SAE database (from the Salix Safety department) before database lock.

All treatment-emergent SAEs will be summarized by body system and preferred term, overall and by treatment group.

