9 STATISTICAL AND ANALYTICAL ISSUES

9.1 Handling of dropouts or missing data

Subjects who prematurely discontinue before the end of the treatment will be contacted via follow-up phone call as frequently as needed. If the patient is found to have an AE or clinically significant laboratory abnormality, the patient will be followed until the event/abnormality is resolved, or until the Investigator determines that further follow-up is no longer medically indicated.

For subjects who discontinue prematurely, the last completed post-baseline assessment will be used as EOT.

Missing data will not be imputed in other analyses unless specified otherwise.

For subjects who terminate early from the study, if the study day of the EOT visit falls into a specific protocol defined scheduled visit window, the EOT visit will be reassigned to that specific scheduled visit for the analyses by protocol defined scheduled visit.

For cases where the start date of an AE is not complete, the assumption is made that the AE is a treatment-emergent event unless there is evidence to the contrary.

For cases where the start or the stop date of medication is not complete, the assumption is made that the medication is a concomitant medication unless there is evidence to the contrary.

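### The SAP's treatment-emergent definition rests on start date alone, so an AE that begins between consent and first dose and worsens on drug under the same record is left out of the TEAE tables

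*SAP*

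**What the plan says.** SAP section 8.2.1 defines the term in one sentence: "A treatment-emergent adverse event (TEAE) is defined as any AE started post-treatment". The only other rule on treatment emergence is in SAP section 9.1, and it also turns on the start date: "For cases where the start date of an AE is not complete, the assumption is made that the AE is a treatment-emergent event". Contrary evidence overrides this default. The protocol lists TEAE as an abbreviation but does not define it.

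On what counts as an AE, protocol section 9.1.1 includes "Exacerbation or worsening of a pre-existing illness" and "Increase in frequency or intensity of a pre-existing episodic event or condition". It also says that a condition present at screening that does not worsen belongs in medical history. Protocol section 9.3.1 sets the collection period: "From the time of informed consent through study completion/withdrawal, including the follow-up period".

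The first safety endpoint in SAP section 2.2.2 is "Incidence of treatment-emergent adverse events (TEAEs"). In SAP Appendix 2, Tables 14.3.1.2 to 14.3.1.7 are all restricted to treatment-emergent events. For serious events, SAP section 8.2.4 says: "All treatment-emergent SAEs will be summarized by body system and preferred term, overall and by treatment group".

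**The concern.** Safety and tolerability are the primary objective, and TEAE incidence is the endpoint listed first for it. An event that was mild before dosing and became severe or serious on drug is one that a safety table should show. Under a start-date rule it is classed by when it began, not by what happened after exposure, and so it does not reach the tables by organ class and preferred term, seriousness, discontinuation, intensity or relationship.

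The wording is also loose. The SAP ties baseline, study day and the medication categories to the first dose, but it does not tie treatment emergence to it.

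**Working it through.** The plan states no figure that can be reproduced here. The check is a comparison of rules, followed by simple arithmetic for scale.

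**1. Can an AE carry a start date before the first dose?** Yes. Collection begins at consent, Screening runs from Day -21 to Day -1 (protocol section 10.1), and AEs since Screening are recorded again at Visit 2 before randomization (protocol section 10.2.1).

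**2. How does the SAP classify each case?**

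| How the event is recorded | TEAE under SAP 8.2.1 and 9.1? |
|---|---|
| New AE with onset after first dose | Yes |
| Pre-existing condition that worsens after dosing, entered as a new AE dated to the worsening | Yes |
| AE with incomplete start date | Yes by default |
| AE with a known start before first dose, ongoing at dosing, that worsens or becomes serious under the same record | No |

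Only the last row is affected. Neither document says whether a site should open a new record or update the existing one when an AE worsens, so which row applies depends on data entry.

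**3. Where does an event in the last row still appear?** In Table 14.3.1.1 (all AEs by treatment group), in Listing 16.2.7.1, and in Listings 16.2.7.2 and 16.2.7.3 if it is serious or leads to withdrawal. It is absent from Tables 14.3.1.2 to 14.3.1.7. Protocol section 11.5 planned organ-class and preferred-term, severity and relationship tabulations of each AE without limiting them to TEAEs. SAP section 8.2.1 also mentions summaries of AEs by preferred term and severity, but Appendix 2 lists no organ-class and preferred-term table for all AEs.

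**4. Scale.** Planned group sizes are 6 SAN-300 patients per cohort and 10 pooled placebo patients (protocol section 11.1). One patient in an event row weighs:

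- SAN-300 cohort: 1/6 = 0.167, or 16.7 percentage points
- Pooled placebo: 1/10 = 0.100, or 10.0 percentage points

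These are the weights of one patient, not estimates of the loss. The overall TEAE percentage changes by that amount only if the patient has no other TEAE.

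**The case against.** The strongest reply is that the protocol makes the worsening itself the AE. For a pre-existing condition, the AE comes into being when the condition worsens; if that happens after dosing, it started after dosing and is a TEAE. This stands for conditions held as medical history and for any worsening entered with its own onset date. It does not cover an AE already opened during Screening and then updated under the same record, because no document tells the site to start a new one.

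Four further points reduce the reach of the problem:

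- Exclusion criteria 6 and 7 bar current active infection and symptomatic viral or bacterial infection in the 14 days before randomization, and dosing follows within 24 hours of randomization. An infection that begins in Screening and turns serious on drug is therefore an unlikely example.
- Incomplete start dates default to treatment-emergent.
- Affected events remain in Table 14.3.1.1 and the listings. With 41 patients randomized (SAP section 3.5), those can be read patient by patient.
- Dose-escalation reviews and stopping rules work from AEs and confirmed events, not from the TEAE flag.

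These make the problem rare and leave it visible to a careful reader. They do not correct the counts in the tables.

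A reader might infer three stronger things that the documents do not support:

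- That every worsened pre-existing condition drops out of the TEAE tables. The reply above shows that this depends on how the event is recorded.
- That post-treatment means after treatment has ended, so that events during dosing are excluded. That reading is strained: Table 14.3.1.4 reports TEAEs leading to discontinuation, which would make little sense under it.
- That the rule must be wrong for conditions merely first found on treatment, which the protocol does count as AEs: "Condition detected or diagnosed after study product administration even though it may have been present prior to the start of the study". AE and TEAE are different sets by design, and whether later detection alone makes an event treatment-emergent is a matter of preference.

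**Conclusion.** The concern holds in a limited form. The SAP's stated rule gives the wrong count for one class of event: an AE with a known start between consent and first dose that increases in severity or becomes serious after dosing without a new record. The loss is from Tables 14.3.1.2 to 14.3.1.7 only.

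The number of such events is likely to be small, and the documents give no basis for estimating it. The conclusion assumes that at least some sites would update an existing AE record; if every worsening were entered as a new AE, nothing would be lost. Because that convention is not written down and the endpoint serves the primary objective, the definition should be corrected.

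**What to change.** In SAP section 8.2.1, define a TEAE as any AE with onset on or after the first dose of study drug, or any AE or condition present before the first dose that worsens in severity or frequency, or becomes serious, after it, through the Exit Visit. This replaces the term post-treatment with an anchor at the first dose. Add that a worsening is dated by the day it worsened. Apply the definition to Tables 14.3.1.2 to 14.3.1.7.

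The cost is a sentence or two in the SAP and a flag in the AE dataset. TEAE counts may rise slightly, which is the conservative direction for a safety study.
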